For Groups 1 through 3 the duration of each subject's participation will be approximately 47 days, including a screening period of up to 30 days, a treatment period consisting of 6 to 7 nights (depending on the admission day) and a follow-up visit, 7 to 10 days after discharge from the treatment period.

For the first 4 subjects in Group 5 (Part 1) participating in the 2-period portion of the study, duration of each subject's participation will be approximately 55 days. These subjects will be given the option to remain at the clinic between samplings for the off dialysis assessment (post dialysis dosing) at the discretion of the Investigator.

For the remaining subjects in Group 5 (Part 2) participating in a single treatment period, duration of each subject's participation will be approximately 47 days.

Subjects may be admitted to the clinic on Day -2 for the Day -1 assessments at the discretion of the Investigator.

Outcome variable(s):

- Pharmacokinetic
 - Primary plasma pharmacokinetic parameters: AUC and C_{max},
 - Secondary plasma pharmacokinetic parameters: CL/F, t_{1/2}, t_{max}, and V_z/F in all subjects; Ae, CL_D, and fe in Groups 1 to 4; A_{d(4-8)}, Cl_R, and fd₍₄₋₈₎ in Group 5 during Period 2

- **Safety**

Adverse events and serious adverse events including severity, vital signs, physical examinations, laboratory parameters, electrocardiograms, and the Columbia-Suicide Severity Rating Scale.

Statistical methods

Tabulations and listings of data for vital signs, physical examinations, clinical laboratory tests, and electrocardiograms will be presented. Results from the Columbia Suicide Severity Rating Scale will be presented separately in a listing only. For clinical laboratory tests, listings of values for each subject will be presented with abnormal or out-of-range values flagged (other than those associated with renal impairment and /or stable chronic condition). Plasma and urine concentration data and the derived pharmacokinetic parameters will be summarized by renal function group using descriptive statistics.

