AE	Adverse event (see definition in Section 6.3.1)
AUC	Area under plasma concentration time curve from zero to infinity
AUC _(0-t)	Area under plasma concentration time curve from zero to last quantifiable time point
AUC ₍₄₋₈₎	Area under plasma concentration time curve from 4 to 8 hours postdose
%AUC _{ex}	Percentage of AUC obtained by extrapolation
BMI	Body Mass Index
BP	Blood pressure
CI	Confidence interval
CL/F	Apparent plasma clearance
CL _D	Dialysate clearance
Cl _R	Renal clearance
C _{max}	Maximum plasma concentration
CPA	Clinical Pharmacology Alliance
CRF	Case Report Form (electronic/paper)
CL _{CR}	Creatinine clearance
CSA	Clinical Study Agreement
CSP	Clinical Study Protocol
CSR	Clinical Study Report
C-SSRS	Columbia-Suicide Severity Rating Scale
CV%	Coefficient of variation (%)
DAE	Discontinuation of Investigational Product due to Adverse Event
DES	Data Entry Site
DMP	Data Management Plan
DMPK	Drug metabolism and pharmacokinetics
DNA	Deoxyribonucleic acid

Abbreviation or special term	Explanation
ECG	Electrocardiogram
ESRD	End stage renal disease
eCRF	Electronic case report form
eGFR	Estimated glomerular filtration rate
f_e	Fraction of dose excreted as unchanged drug into urine
$f_{d(4-8)}$	Fraction of dose extracted unchanged into the dialysate over the dialysis period from 4 hours postdose to 8 hours postdose
FSH	Follicle stimulating hormone
GCP	Good clinical practice
GMP	Good manufacturing practice
HIV	Human immunodeficiency virus
ICF	Informed Consent Form
ICH	International Conference on Harmonisation
IP	Investigational Product
IRB	Institutional Review Board
LIMS	Laboratory Information Management System
LH	Luteinizing hormone
LLOQ	Lower Limit of Quantification
MDRD	Modification of Diet in Renal Disease
OAE	Other Significant Adverse Event (see definition in Section 11.1.1)
pCRF	paper case report form
PGx	Pharmacogenetic research
PI	Principal Investigator
PK	Pharmacokinetics
PR(PQ)	ECG interval measured from the onset of the P wave to the onset of the QRS complex.
QRS	ECG interval measured from the onset of the QRS complex to the J point.
QT	ECG interval measured from the onset of the QRS complex to the end of the T wave
QTcF	QT interval corrected for heart rate using Fridericia's formula
RR	The time between corresponding points on 2 consecutive R waves on ECG
SAD	Single ascending dose
SAE	Serious adverse event (see definition in Section 6.3.2).

Abbreviation or special term	Explanation
SD	Standard deviation
SOP	Standard Operating Procedure

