3.2 Rationale for study design, doses and control groups

The purpose of this study is to determine if renal impairment will affect the PK of TC-5214. The study is designed using the principals embodied in the Food and Drug administration guidance on drug renal impairment studies ([Cockcroft 1976](#)).

For control subjects with normal renal function and subjects with mild renal impairment, a 8 mg dose of TC-5214 was chosen because it is the highest daily dose that will be administered in Phase III trials and was shown to be well tolerated in healthy subjects in previous studies. For subjects with moderate and severe renal impairment, to minimize the effects of compensatory changes such as significant hypotension, a 2 mg dose will be administered.

In order to avoid bias due to demographic differences between the control subjects with normal renal function and subjects with renal impairment, the control group will be matched to the mean demographic characteristics of the **3** renal impairment groups with an allowable variability in age of +/- 10 years and in BMI of $\pm 3 \text{ kg/m}^2$. Sex will be matched to achieve similar distribution between male and female subjects. Only control subjects with stable chronic medical conditions will be included.

Based on available data to date, the mean terminal half-life ($t_{1/2,\lambda_z}$) of TC-5214 in human plasma is approximately 8 to 9 hours. Based on limited interim PK data in 2 subjects with moderate impairment, and 2 subjects with ESRD, renal impairment has been shown to increase the half-life of TC-5214 by approximately 3 and 10 fold, respectively.

For Groups 1 to 3, the study design has been updated to extend the sampling period to 120 hours postdose to adequately characterize the elimination phase of TC-5214 and more accurately determine TC-5214 PK parameters (eg $t_{1/2,\lambda_z}$, AUC, and CL/F). For Group 5 it was determined that a single dose of TC-5214 administered after the completion of a dialysis session, with the collection of blood samples for PK through 120 hours postdose (including a 4 hour dialysis session beginning approximately 72 hours postdose) would enhance patient safety.

The PK profile in patients with severe renal failure will be extrapolated from the data in subjects on dialysis obtained between their dialysis sessions, thus subjects with severe renal impairment (eGFR <30 mL/min) will not be recruited for this study.

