6.4.1.1 Blood Samples

Blood samples (approximately 6 mL, split into 2 tubes, collected in K2 EDTA tubes) for determination of TC-5214 in plasma will be taken on the days presented in the study plans [Table 1](#) and [Table 2](#).

Part 1:

For Group 1, Group 2, and Group 3 blood PK samples will be collected at predose, 1, 1.5, 2, 2.5, 3, 4, 6, 8, 12, 24, 36, 48, and 72 hours postdose.

For Group 5, Part 1, blood PK samples will be collected at predose, 1, 1.5, 2, 2.5, 3, 4, 6, 8, 12, 24, 36, 48, and 72 hours postdose. For Treatment Period 2, the timing of sample collections is the same as for Treatment Period 1, however, the sample scheduled for collection at 4 hours must be collected immediately before dialysis start, and the sample scheduled at 8 hours must be collected immediately after dialysis completion rather than strictly adhering to the scheduled sampling times at 4 and 8 hours. For Treatment Period 2, the blood samples during and surrounding the hemodialysis session will be collected from predialyzer lines.

Part 2:

For Part 2, Group 1, Group 2, and Group 3, blood PK samples will be collected at predose, 1, 1.5, 2, 2.5, 3, 4, 6, 8, 12, 24, 36, 48, 72, 96, and 120 hours postdose.

For Group 5, Part 2, blood PK samples will be collected at predose, 1, 1.5, 2, 2.5, 3, 4, 6, 8, 12, 24, 36, 48, 72, 74, 76, 96, and 120 hours postdose. The sample scheduled for collection at 72 hours must be collected immediately before dialysis start, and the sample scheduled at 76 hours must be collected immediately after dialysis completion rather than strictly adhering to the scheduled sampling times. Blood samples during and surrounding the hemodialysis session will be collected from predialyzer lines.

The date and time of collection of each sample will be recorded on the pCRF. For blood volume, see Section 7.1.

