11.2 Calculation or derivation of pharmacokinetic variables

The PK analyses of the TC-5214 plasma, urine, and dialysate concentration data will be performed at [REDACTED]. Pharmacokinetic analyses will be conducted according to [REDACTED] SOPs for PK analyses. The actual sampling times will be used in the PK parameter calculations. Pharmacokinetic parameters will be derived using noncompartmental methods with WinNonlin[®] Professional Version 5.2, or higher, (Pharsight Corp., Mountain View, California). All PK computations will be performed using WinNonlin Professional[®] 5.2, or higher; or SAS[®] Version 9.1, or higher (SAS Institute, Inc., Cary, North Carolina). Graphics may be prepared with SAS Version 9.1, or higher; SigmaPlot[®] 9.0, or higher (Systat Software, Inc., San Jose, California); or WinNonlin Professional[®] 5.2, or higher. Nominal times will be used for any interim PK analyses, if applicable.

Where possible, the following plasma PK parameters will be determined for TC-5214:

- Maximum plasma concentration (C_{max} , ng/mL), obtained directly from the observed concentration versus time data

- Time to maximum plasma concentration (t_{\max} , h), obtained directly from the observed concentration versus time data
- Terminal rate constant (λ_z). Visual assessment will be used to identify the terminal linear phase of the concentration-time profile. A minimum of 3 data points, with an Rsq of greater than or equal to 0.8 will be used for determination.
- Terminal half-life ($t_{1/2\lambda_z}$, h)
- Area under the plasma concentration-time curve from zero to the time of the last measurable concentration [$AUC_{(0-t)}$]
- Area under the plasma concentration-time curve from 4 to 8 hours [$AUC_{(4-8)}$] to match the dialysis period, Group 5, Treatment Period 2, Part 1, only
- Area under the plasma concentration-time curve from 72 to 76 hours [$AUC_{(72-76)}$] to match the dialysis period, Group 5, Part 2, only
- Area under the plasma concentration-time curve from zero to infinity (AUC) calculated by linear up/log down trapezoidal summation and extrapolated to infinity by addition of the last quantifiable concentration divided by the elimination rate constant: $AUC_{(0-t)} + C_{\text{last}}/\lambda_z$. If the extrapolated area ($C_{\text{last}}/\lambda_z$) is greater than 30% of AUC, then AUC will not be reported
- Apparent plasma clearance (CL/F, L/h)
- Apparent volume of distribution (V_z/F , L)

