12.2 Methods of statistical analyses

12.2.1 General Principles

The statistical analysis will be performed at [REDACTED], using [REDACTED] Standard Operation Procedures and Work Instructions.

Study and PK data will be presented by renal function group. Safety data for all TC-5214 treated subjects combined will also be presented.

Since no planned formal testing will be performed in this study, and the confidence intervals that will be calculated are only for descriptive purposes, no corrections for multiplicity will be used.

Missing data will be result in a reduced sample size for that parameter. Since the statistical analyses will be predominantly presentations in tables and individual data listings, no action will be taken to handle missing data.

A volunteer who withdraws prior to the last planned observation in a study period will be included in the analyses up to the time of discontinuation.

Quantitative continuous variables will be summarized using descriptive statistics, including the number of subjects (n), mean, standard deviation (SD), median, minimum (min), and maximum (max) values. Additionally, for PK parameters, (except for t_{\max}), geometric means and geometric coefficient of variation (CV%) will be reported. The geometric mean is calculated as the exponential of the arithmetic mean calculated from data on a log scale. The CV% is calculated as $100 \cdot \sqrt{(\exp(s^2) - 1)}$ where s is the standard deviation of the data on a log scale. Mean, SD, geometric mean and CV% will not be calculated for t_{\max} .

Categorical variables (eg, sex) will be summarized in frequency tables (frequency and proportion of subjects in analysis set).

In general, descriptive statistics will follow the rounding convention in [REDACTED] Global SOPs.

Baseline characteristics will be summarized across all subjects.

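### On the protocol's own ESRD half-life, the 30% extrapolation rule suppresses the primary AUC in every Part 1 dialysis profile and may suppress it in Part 2

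*Supplement*

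**What the plan says.** The synopsis names AUC and Cmax as the primary plasma parameters, and the abbreviation list defines AUC as "Area under plasma concentration time curve from zero to infinity". Section 11.2 obtains it by adding C_last/λz to AUC(0-t), and withholds it when the added part "is greater than 30% of AUC, then AUC will not be reported".

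Section 3.2 states that the mean terminal half-life "of TC-5214 in human plasma is approximately 8 to 9 hours". From interim data in 2 moderate and 2 ESRD subjects it adds that "renal impairment has been shown to increase the half-life of TC-5214 by approximately 3 and 10 fold, respectively".

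Section 6.4.1.1 ends Group 5 sampling in Part 1 at 72 h in both periods ("36, 48, and 72 hours postdose. For Treatment Period 2, the timing of sample collections is the same as for Treatment Period 1"). In Part 2 it ends at 120 h, with a dialysis session at about 72 to 76 h.

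Section 12.2.3 uses AUC in three places: the eGFR regression (for Group 5, Part 1 Period 1 and Part 2), the exploratory ANOVA, and the paired t-test between the two Part 1 periods. It names no substitute when AUC is withheld. Section 12.2.1 says only: "Missing data will be result in a reduced sample size for that parameter".

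**The concern.** The reporting rule and the sampling horizon do not fit together in the group where the largest effect is expected. An ESRD half-life of 80 to 90 h is longer than the whole Part 1 sampling window, so more than half of the AUC lies beyond the last sample. The amendment's rationale acknowledges heavy extrapolation in renal impairment and lengthens sampling for later subjects, but the 30% rule still stands in the current Section 11.2.

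At stake are the low-eGFR end of the primary AUC regression, the corresponding ANOVA contrast, and the AUC part of the dialysis comparison. Section 3.2 also intends to extrapolate the profile in severe impairment from the between-dialysis ESRD data. The loss would not be random: an AUC survives the rule when the half-life is shorter or when dialysis removed more drug. Dropping the rest would tend to understate the effect of lost renal function.

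**Working it through.** The plan states no extrapolated share, so there is no figure to reproduce. The inputs are:

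- Normal half-life 8 to 9 h, about 10-fold in ESRD and about 3-fold in moderate impairment (Section 3.2): 80 to 90 h and 24 to 27 h.
- Last sample T: 72 h in Part 1, 120 h in Part 2 (Section 6.4.1.1).
- Group 5: 8 planned (synopsis), of whom the first 4 have two periods (Section 3.1.1.2). That is 4 × 2 = 8 Part 1 profiles and 8 − 4 = 4 Part 2 profiles, 12 in all. The regression uses 4 (Part 1 Period 1) + 4 (Part 2) = 8.

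**Share extrapolated.** Under first-order decline, (C_last/λz)/AUC = 2^(−T/t½). The longest half-life that meets the rule is T·ln 2 / ln(1/0.3).

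| | T = 72 h | T = 120 h |
|---|---|---|
| t½ = 80 h | 53.6% | 35.4% |
| t½ = 85 h | 55.6% | 37.6% |
| t½ = 90 h | 57.4% | 39.7% |
| Longest t½ meeting 30% | 41.5 h | 69.1 h |

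First-order absorption with an assumed rate constant of 0.5 to 2 per h adds at most about 1 percentage point. In the moderate group the share is 12.5 to 15.7% at 72 h and 3 to 5% at 120 h. At 8 to 9 h it is below 0.5% at 72 h.

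**Dialysis inside the profile.** Let the 4 h session lower concentration by a fraction E, which the documents do not give. With k = ln 2/t½ and kd = −ln(1 − E)/4, add the areas before, during and after the session and divide C_last/k by the total. Worked case for Part 2 at t½ = 80 h, E = 0.30 and starting concentration 1:

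- k = 0.00866 and kd = 0.0892. C(72) = 0.536, C(76) = 0.375, C(120) = 0.256.
- Areas: 53.6 (0–72 h), 1.8 (72–76 h), 13.7 (76–120 h), tail 29.6.
- Share = 29.6/98.7 = 30%.

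| E | Part 2, t½ 80 to 90 h | Part 1 Period 2, t½ 80 to 90 h |
|---|---|---|
| 0.10 | 34–38% | 53–57% |
| 0.20 | 32–36% | 53–57% |
| 0.30 | 30–34% | 53–57% |
| 0.40 | 27–31% | 52–56% |
| 0.50 | 25–28% | 51–55% |

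Part 2 falls to 30% at E = 0.30, 0.38 and 0.44 for half-lives of 80, 85 and 90 h. Part 1 Period 2 is still at 39 to 43% with E = 0.90.

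**Counts at 80 to 90 h.** Part 1: 8 of 8 profiles suppressed, so 0 of 4 pairs for the t-test. Regression: at least 4 of 8 ESRD values lost, and all 8 if dialysis removes little. All profiles: 8 to 12 of 12.

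**What AUC(0-72) would show.** With constant volume, a true 10-fold AUC ratio becomes 10 × (1 − 0.536)/(1 − 0.002) = 4.65 for 80 h against 8 h, and 10 × (1 − 0.574)/(1 − 0.004) = 4.3 for 90 h against 9 h.

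**The case against.** A reader might infer that the rule removes most or all ESRD subjects from the primary regression. The documents do not support that. Half of the ESRD values in the regression come from Part 2, and their fate turns on a dialysis extraction figure that is not given. The majority count is reached only by including Period 2 profiles, which the regression does not use.

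The 10-fold multiplier is approximate and comes from 2 subjects. With an assumed between-subject CV of 30 to 50% around 85 h, 24 to 33% of Part 2 subjects would fall below the 69 h limit even with no dialysis removal. This qualification stands. It hardly touches Part 1, where only 1 to 6% would fall below 41 h.

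It is also tempting to say that the R-squared requirement for λz makes matters worse. That cannot be quantified here. Residual error is not stated, and the terminal window is chosen by eye. Rejection runs from near 0% to about 60% depending on what is assumed.

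Nor is the hemodialysis objective lost. Dialysate clearance uses AUC over the session, and the fraction extracted needs no AUC. Cmax is untouched, AUC(0-t) is derived, and additional parameters are permitted. But Section 12.2.3 names none of these as a replacement for AUC, and AUC(0-t) would span 72 h in some subjects and 120 h in others.

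Finally, the rule is a reliability safeguard, and an AUC that is more than half extrapolated is a weak number. That is a reason to flag it and to give an observed measure beside it. Leaving gaps in a primary analysis is a poorer answer.

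**Conclusion.** The point holds, firmly for Part 1 and conditionally for Part 2. If the plan is followed as written and the ESRD half-life is near the protocol's 80 to 90 h, no Part 1 Group 5 AUC is reportable, the paired AUC test cannot be run, and at least half of the ESRD values leave the AUC regression and ANOVA. Whether the other half survive depends on half-life and on how much the 72 to 76 h session removes, so the missingness is informative.

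This rests on first-order decline, on the 2-subject half-life figure, and on a λz that reflects off-dialysis elimination. The plan does not say which samples define λz in Part 2. A fit through 72, 96 and 120 h across a 20% dialysis drop would give 25 to 27% and pass, but with a falsely short half-life of 55 to 59 h. The study is exploratory and its intervals are descriptive, which limits the consequence to estimation. Estimating the renal effect is, however, the primary objective.

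**What to change.** In Section 11.2, replace non-reporting with reporting of every estimable AUC, flagged with the extrapolated percentage that the plan already calculates. Add a sensitivity analysis that excludes values above 30%.

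In Section 12.2.3, prespecify observed AUC(0-72) as an exposure measure for the regression and ANOVA, and as the measure for the Part 1 paired comparison. The sampling schedule supplies it in every group and part. In Part 1 Period 1 and in Part 2 it ends before the next dialysis; in Part 1 Period 2 it includes the session, which is what that comparison needs.

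The cost is wording and a few extra model runs, with no new samples or subjects. Two drawbacks should be stated in the plan. Flagged Part 1 ESRD values of AUC to infinity are more than half extrapolated. AUC(0-72) compresses the contrast, showing a true 10-fold ratio as about 4.3- to 4.65-fold. Neither measure should be read without the other.

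A compartmental model with a separate dialysis clearance is optional supportive work. Taking AUC as dose over CL/F from it gives off-dialysis exposure, so it would not supply the Period 2 AUC.

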12. STATISTICAL METHODS AND SAMPLE SIZE DETERMINATION BY [REDACTED]

12.1 Description of analysis sets

12.1.1 General principles

The statistical analysis will be performed by [REDACTED] using SAS[®], Version 9.1 or higher. The analysis of data will be based on different subsets according to the purpose of analysis, ie, for safety and PK, respectively. The decision regarding validity of data for each of the analysis sets will be based on a blind review of data.

The as-treated principle will be applied to all evaluations; ie, volunteers who received another treatment than the one assigned will be analyzed as belonging to the actual treatment group.

12.1.2 Safety analysis set

All subjects who received at least 1 dose of IP and for whom any postdose data are available will be included in the safety population.

12.1.3 Pharmacokinetic Analysis Set

The PK analysis set will be a subset of the safety analysis set and will include only subjects who receive TC-5214 and have at least 1 postdose PK measurement without important protocol deviations or violations thought to significantly affect the PK. A strategy for dealing with data affected by protocol violations and deviations will be specified prior to clean file by the study team (eg, the CPA physician, and AstraZeneca [REDACTED] pharmacokineticists and statisticians).

12.2 Methods of statistical analyses

12.2.1 General Principles

The statistical analysis will be performed at [REDACTED], using [REDACTED] Standard Operation Procedures and Work Instructions.

Study and PK data will be presented by renal function group. Safety data for all TC-5214 treated subjects combined will also be presented.

Since no planned formal testing will be performed in this study, and the confidence intervals that will be calculated are only for descriptive purposes, no corrections for multiplicity will be used.

Missing data will be result in a reduced sample size for that parameter. Since the statistical analyses will be predominantly presentations in tables and individual data listings, no action will be taken to handle missing data.

A volunteer who withdraws prior to the last planned observation in a study period will be included in the analyses up to the time of discontinuation.

Quantitative continuous variables will be summarized using descriptive statistics, including the number of subjects (n), mean, standard deviation (SD), median, minimum (min), and maximum (max) values. Additionally, for PK parameters, (except for t_{\max}), geometric means and geometric coefficient of variation (CV%) will be reported. The geometric mean is calculated as the exponential of the arithmetic mean calculated from data on a log scale. The CV% is calculated as $100 \cdot \sqrt{(\exp(s^2) - 1)}$ where s is the standard deviation of the data on a log scale. Mean, SD, geometric mean and CV% will not be calculated for t_{\max} .

Categorical variables (eg, sex) will be summarized in frequency tables (frequency and proportion of subjects in analysis set).

In general, descriptive statistics will follow the rounding convention in [REDACTED] Global SOPs.

Baseline characteristics will be summarized across all subjects.

